A Pilot Study Assessing the Effects of Sublingual Sufentanil 30 µg on Postoperative Recovery from Ambulatory Surgery

Principal Investigator	[name], MBA, FASA Cleveland Clinic, Fairview Hospital Anesthesia Institute Department of Outcomes Research [name] Office: (216) [contact] Email: [contact]
Research Conduct Oversight	Cleveland Clinic Institutional Review Board
IRB #	20-642
Funded by an Investigator Initiated Research Grant from:	AcelRx Pharmaceuticals [name] Email: [contact]
Interventions	Sufentanil 30 µg versus 50 µg IV fentanyl

Version 20: November, 2020

Study Summary

Title	A Pilot Study Assessing the Effects of Sublingual Sufentanil 30 µg on Postoperative Recovery from Ambulatory Surgery
Methodology	Randomized trial
Study Duration	6 months
Single vs. Multicenter Design	Single center
Objectives	
A pilot study to evaluate the effect of incorporating sublingual sufentanil into our perioperative opioid regimen for ambulatory orthopedic surgery. The results will help us estimate treatment effect and determine sample size for a subsequent full-scale clinical trial.
 
Primary Endpoint: total amount of fentanyl consumed during PACU admission.
 
Secondary Endpoints: 1) phase I recovery time; and, 2) time to fitness for discharge.
 
Exploratory Endpoints 1) intraoperative hemodynamics; 2) intraoperative opioid use; 3) intraoperative sevoflurane use; 4) postoperative pain; 5) postoperative sedation and cognitive recovery 6) time to first request for analgesia; and, 7) incidence of nausea and vomiting between the end of anesthesia and hospital discharge.

Number of Subjects	Total randomized sample: 75 plus \leq 6 pilot patients.
Main Inclusion and Exclusion Criteria	
Inclusion Criteria: patients aged \geq 18; having elective outpatient knee arthroscopy surgery without ligamentous repair.
 
Exclusion Criteria: opioid tolerance and medical contraindication.

Treatment Groups	
 - Intervention group: 30 µg tablet of sublingual sufentanil preoperatively and fentanyl placebo at induction of anesthesia. - Control group: placebo sublingual sufentanil preoperatively and 50 µg fentanyl at induction of anesthesia
Data and Safety Monitoring	Responsibility for monitoring data quality and ongoing safety of subjects will be that of AcelRx, the PI, and study coordination staff.

Background and Rationale:

Opioid medications are indicated and frequently used in the treatment of acute moderate-to-severe pain. Delivering timely, safe, and efficient analgesia in fast-paced care environments, such as the emergency room or ambulatory surgery center, can present challenges where intravenous opioid formulations, though fast-acting, carry disadvantages non-conducive to patient safety and care efficiency. For example, intravenous delivery require insertion of an IV catheter and connection to tubing and delivery apparatus. IV's, in addition to the discomfort and minor risks associated with any invasive procedure, also create a means by which one of the most common medication dosing errors is created [1-3]. Human factors concerning technical delivery of drug exist for understandable reasons – the similar appearance of many IV liquids, the potential for misreading labels, the need for calculations, the accuracy required for drawing medication into syringes or programming pumps, etc. – but the pharmacy of IV opioids tends to make their use in the acute ambulatory setting challenging for reasons intrinsic to the medication.

Compounding the chances for error is the pharmacokinetic profile of commonly administered IV analgesics, such as fentanyl. Their rapid plasma fluctuations, corresponding to onset and offset, make them difficult to titrate acutely for analgesia and often require frequent re-dosing. Additionally, the delayed plasma response of their active metabolites not only contribute to the phenomenon of dose stacking, but also account for side effects that can be both dangerous and unpleasant to the patient. Nausea/vomiting, itching, ileus, etc., all negatively impact patient experience as well significantly delay their discharge from facility and increase the cost of care.

A benefit of IV delivery in higher acuity out-patient settings is rapid onset and relief of pain as compared to oral formulations. But many of the traditional advantages of intravenous drug and fluid administration do not apply. The ability to continue infusions for several days; the ability to administer large volumes of fluids and blood products; the ability to administer several other IV medications; etc. – these are some of the typical gains that help offset the drawbacks of IV addressed previously. But none of these apply to the care of patients undergoing common outpatient surgical procedures or ER visits that don't require admission but still entail a significant amount of pain. For these care units, historically, one could argue that the selection of IV opioids is less about the full utilization of a line that offsets its risks and drawbacks, but rather, is a reluctant choice made despite them without an equally effective alternative analgesic that can be administered differently.

Sublingual sufentanil, an under-the-tongue opioid formulation, offers a unique solution that addresses many context-specific pain treatment problems. Importantly, the sublingual form is absorbed directly into veins that drain the tongue, not by oral digestion, and thus approximates intravenous delivery without requiring intravenous access. However, sublingual administration differs from a pure intravenous delivery in a crucial way. In stark contrast to IV, sublingual sufentanil creates a depot in sublingual fat that is released slowly which blunts peak serum concentration, lessening the chance for respiratory depression (figure below).

[figure not shown]

Figure Legend:

Plasma concentration profile (mean, SD of venous concentrations) for 30 µg of sufentanil administered to 39 subjects in study SAP101. Colors indicate dose and route of administration. Cp = plasma concentration; IV = intravenous; SL = sublingual.

Date of download: 11/7/2019

Copyright © 2019 American Society of Anesthesiologists. All rights reserved.

Slow release from sublingual fat depots prolongs the drug's effect, typically providing effective analgesia lasting up to 3 hours – a sufficient window within which to treat pain in the ER or for ambulatory surgery. Sufentanil has no active metabolites that “stack” its effects or contribute to side effects. Available literature remains sparse, making it well worth examining the potential benefits of sublingual sufentanil on post-operative recovery, especially the extent to which sublingual sufentanil might provide safe and effective analgesia for minor ambulatory surgery.

Objectives:

Objective: A pilot study to evaluate the effect of incorporating sublingual sufentanil into our perioperative opioid regimen for ambulatory orthopedic surgery. The results will help us estimate treatment effect and determine sample size for a subsequent full-scale clinical trial.

Primary Endpoint: total amount of fentanyl consumed during PACU admission.

Secondary Endpoints: 1) phase I recovery time; and, 2) time to fitness for discharge.

Exploratory Endpoints: 1) intraoperative hemodynamics 2) intraoperative opioid use; 3) intraoperative sevoflurane use 4) postoperative pain; 5) time to first request for analgesia;

and, 6) incidence of nausea and vomiting between end of anesthesia and hospital discharge.

Safety Monitoring: all adverse events will be recorded as detailed below.

Methods

A pilot for a randomized, controlled trial.

Subject selection

Study coordinators at Fairview Hospital will call patients scheduled for knee arthroscopy at least 1 day prior to the day of surgery to notify them of eligibility with the use of an IRB approved phone script (to be submitted in a supplemental document not contained in the protocol). Interested patients will be met in the facility on the day of surgery to provide private consultation, wherein the purpose, objectives, risks, and benefits of the investigation will be thoroughly addressed. Signed copies of the consent form will be stored on-site in a secure location.

Team consensus from the PI, anesthesiologist, and the patient's surgeon regarding research enrollment will be obtained. Each team member must agree as to the suitability for research and safety of the intervention as it pertains to each case. Communication will be documented in the electronic medical record system.

Inclusion Criteria:

- Adults aged ≥ 18 years;
- Scheduled for elective knee arthroscopy without anticipated ligamentous repair;
- Planned general anesthesia without a regional block or wound infiltration with local anesthesia;
- Planned day-of-surgery discharge.

Exclusion Criteria:

- Opioid tolerance defined by ≥ 15 mg of oral morphine daily or equianalgesic dose of another opioid within 30 days of surgery;
- Known hypersensitivity to sufentanil or components of DSUVIA;
- Patients with an allergy or hypersensitivity to opioids.
- Pregnancy or actively breastfeeding;
- Patients who are currently taking monoamine oxidase inhibitors (MAOIs) or have taken MAOIs within 14 days of the first dose of study drug;
- Patients with a medical condition that, in the Investigator's opinion, could adversely impact the patient's participation or safety, conduct of the study, or interfere with the pain assessments, including chronic pain or active infection.

Protocol

Preoperative Assessment:

- Baseline Blessed Orientation-Memory-Concentration (BOMC).

- Pain Catastrophizing Scale
- PEG 3 Item Scale

Preoperative Medication:

Participating patients will be given 2 mg of midazolam to alleviate pre-procedure anxiety unless the drug is considered contra-indicated by the attending anesthesiologist. Patients will be given 1 g oral acetaminophen with a sip of water about 30 minutes before induction of anesthesia.

Randomization:

75 patients will undergo 1:2 randomization without stratification to either placebo or sufentanil (25 placebo patients and 50 sufentanil patients). The randomization list will be prepared by trial statisticians and administered by the research pharmacy. Allocation will be concealed until just before induction of anesthesia by a web-based system. Patients will be randomized to:

Intervention: Sufentanil 30 μ g tablet sublingually prior to induction of anesthesia and placebo fentanyl at induction.

Control: Placebo sublingual sufentanil prior to induction of anesthesia and 50 μ g IV fentanyl at induction.

Timing of Administration for Sufentanil/Placebo:

As the method of airway management requires different analgesic thresholds, administration of sufentanil will be staggered accordingly:

In the event that the airway will be secured via laryngeal mask, the sufentanil tablet/placebo will be administered approximately 15 minutes prior to induction.

In the event that the airway will instead be secured via endotracheal tube, the sufentanil tablet/placebo will be administered approximately 30 minutes prior to induction just following the dose of oral acetaminophen.

Standardized Anesthetic Regimen:

General anesthesia will be induced with IV propofol, dose per judgment of the attending anesthesiologist. The airway will be secured with a laryngeal mask airway or endotracheal tube. Anesthesia will be maintained with sevoflurane, titrated to a Bispectral Index (BIS) of 40-60. 4 mg of IV ondansetron will be given intravenously before emergence from anesthesia.

No NSAIDs or other opioids will be given during surgery unless clinically indicated. Post-operatively, patients will follow the standard of care (SOC) protocol for recovery analgesia that includes PRN acetaminophen and IV fentanyl injections. Patients will be given 500 mg acetaminophen for reported pain scores in the range of 1-3. For pain in the range of 4-10, 25 μ g IV fentanyl can be given at 5-minute intervals. No long-acting opioids will be given.

Treatment Blinding:

The research pharmacist will be the designated unblinded member of the team responsible for preparation of treatment and corresponding placebo. Blinded study coordinators will receive from pharmacy: 1) a sublingual applicator loaded with either active sufentanil or matching

placebo; and, 2) an IV syringe containing either fentanyl or fentanyl placebo. These will be delivered to perioperative personnel for use as described above.

Post-Operative Recovery Assessments:

- Pain Score: every 15 minutes for the first hour after PACU admission and then 30 minute intervals until PACU discharge.
- Richmond Agitation Sedation Score (RASS) completed at intervals above until patient is non-sedated. Afterwards, BOMC is conducted in place of RASS.
- Blessed Orientation-Memory-Concentration (BOMC) test, at intervals above or until baseline is achieved.
- Postoperative Nausea and Vomiting (PONV) Intensity Scale prior to discharge.

Post Discharge

Patients will be called at post-operative day 7 (POD7) to assess for interim adverse events.

Measurements

- 1) Total consumption of fentanyl: the cumulative μg dose of fentanyl received between arrival to and discharge from PACU per patient's Medication Administration Report.
- 2) Phase I recovery time: per anesthesia record, the time documented for end-of-case will be taken as the time that the patient entered phase I recovery. Recovery will be considered complete at the time an order is placed for progression to phase II, limiting the extent to which PACU traffic and bed availability can affect the assessment. Determination of phase I discharge readiness is made at regular intervals according to criteria detailed in Cleveland Clinic's Routine Postoperative Patient Care Protocol.
- 3) Time to Fitness for PACU Discharge: will be determined per facility protocol-scheduled assessments using the CCF Phase II Discharge Scoring tool. The time that the minimum acceptable score of 14 is achieved will be recorded.
- 4) Intraoperative Hemodynamics: the incidence of induction hypotension as measured by the area under a MAP of 65 mmHg during the initial 15 minutes of anesthesia.
- 5) Intraoperative IV Opioid Use: amount of clinically indicated opioid outside of standardized anesthetic regimen, in oral morphine equivalents (OME).
- 6) Intraoperative Sevoflurane Use
- 7) Postoperative Pain Score: measured as 0-10 Verbal Response Scores conducted at rest.
- 8) Postoperative Sedation and Cognitive Recovery: there is no validated scoring tool which assesses cognitive recovery after anesthesia in ambulatory surgery. Still, there may be value in trying to elucidate an approximation in this trial given anecdotal evidence that sufentanil reduces the use of intraoperative anesthetic gas and promotes faster recovery to arousal/cognitive baseline. To measure this, first RASS will be utilized by a member of the staff to capture early recovery while patients are less able (or unable) to answer questions. When a patient is no longer

sedated according to RASS and able to “spontaneously pay attention”, the BOMC test will be administered to measure improvements in executive cognitive functions thereafter.

9) Time to first request for analgesia: defined as the time from official case end until the first recorded Verbal Response Pain Score of greater than 4 (necessitating intervention).

10) Incidence of post-operative nausea/vomiting: the number of cases identified as clinically significant PONV using the PONV Intensity Scale.

Opioid-related adverse events will be recorded, including nausea and vomiting and respiratory depression requiring treatment (naloxone, airway support, etc.). Adverse event reporting will proceed in accordance with Cleveland Clinic IRB-60 Policy.

Data analysis

Randomized groups will be compared for baseline balance using standard descriptive statistics and the standardized difference (difference in means or proportions divided by the pooled standard deviation).

Firstly, we will describe and plot the distribution of the primary outcome, which is the total amount of fentanyl consumed during PACU. If the distribution is approximately normal, we will calculate the standard deviation directly; if it is log-normal, we will estimate the geometric mean and the coefficient of variance. Then we will assess the effect of treatment using t-test or linear regression after log transformation as appropriate.

To assess the treatment effect on Phase I recovery time and time to fitness for discharge, we will use t-test or Wilcoxon test, depending on the distribution of the outcome variables. The difference in mean or median will be reported with 95% confidence interval.

Exploratory outcomes will be summarized by treatment group. The pain level will be summarized by time and the difference across all times will be summarized as difference in mean with 95% confidence interval; the difference in time to first request for analgesia will be summarized as median difference with 95% confidence interval; difference in nausea and vomiting will be summarized as relative risk with 95% confidence interval.

The overall alpha will be 0.05 for both primary and secondary outcomes. Thus the significance level is 0.05 for the primary outcome and 0.025 (i.e. 0.05/2, Bonferroni correction) for all secondary outcomes.

Sample size and power consideration

As this is a pilot study, we aim to estimate the standard deviation of various outcomes, but not to achieve statistical significance. Pilot trial recommendations are usually for 30 to 70 patients [5]. We thus propose to enroll 75 patients, excluding up to 6 pilot patients.

References:

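### Planned airway sets the tablet's lead time and is known before dosing, yet no comparison uses it: a modest, cheaply avoided loss of precision, not a bias

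*Combined protocol and SAP*

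**What the plan says.** The Randomization section states that "75 patients will undergo 1:2 randomization without stratification to either placebo or sufentanil", giving "25 placebo patients and 50 sufentanil patients". The next section, Timing of Administration for Sufentanil/Placebo, makes dosing depend on the airway: "As the method of airway management requires different analgesic thresholds, administration of sufentanil will be staggered accordingly". For a laryngeal mask, "the sufentanil tablet/placebo will be administered approximately 15 minutes prior to induction". For an endotracheal tube, "the sufentanil tablet/placebo will be administered approximately 30 minutes prior to induction just following the dose of oral acetaminophen". The Standardized Anesthetic Regimen allows either device ("The airway will be secured with a laryngeal mask airway or endotracheal tube") and gives no expected mix.

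For the primary outcome, PACU fentanyl, the Data analysis section says: "Then we will assess the effect of treatment using t-test or linear regression after log transformation as appropriate". For phase I recovery time and time to fitness for discharge, "we will use t-test or Wilcoxon test, depending on the distribution of the outcome variables". It names no airway term, airway-stratified estimate or by-airway summary. Baseline balance is to be described with standardized differences, but the variables are not listed and no action follows from an imbalance.

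Under Objectives, the results are to inform the treatment effect and sample size of a full trial. Under Sample size and power consideration, the aim is to estimate SDs rather than to reach significance.

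**The concern.** The timing rule cannot be followed unless the airway plan is settled by about 30 minutes before induction, the earlier of the two dosing times. The trial therefore has a two-level factor that is known before the tablet is given and that the protocol itself ties to analgesia. Neither the randomization list nor the analysis uses it.

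Two things are at stake. If airway type is related to PACU fentanyl or recovery time, a chance difference in airway mix between 25 and 50 patients adds error to the treatment difference that an adjusted analysis would remove. The between-airway variation also stays in the SD carried forward to size the next trial.

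**Working it through.** **Inputs from the documents.** N = 75 with 1:2 allocation: 75/3 = 25 control and 75 × 2/3 = 50 sufentanil, which reproduces the stated split. The plan has no power calculation to reproduce.

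**Assumed inputs.** The documents give neither of these:
- Endotracheal share p: 20%, 30% or 50%, that is K = 15, 22 or 38 of 75.
- Outcome gap g between airways, in within-airway SD units: 0.5, with a range of 0.25 to 1.0.

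**Step 1: chance imbalance.** With a fixed 25/50 split, the number of intubated controls x is hypergeometric (25 drawn from 75, of whom K are intubated). The difference in shares is x/25 − (K − x)/50. Its SD is 0.06 × √[25 · p(1 − p) · 50/74]. For p = 0.20 this is 0.06 × √2.703 = 0.0986.

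**Step 2: chance error in the treatment difference.** The 95% range is ±1.96 × (SD of the difference in shares) × g. For p = 0.20 and g = 0.5 it is 1.96 × 0.0986 × 0.5 = 0.097 SD.

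**Step 3: inflation of the pooled SD.** The factor is √[1 + g²p(1 − p)]. For p = 0.20 and g = 0.5 it is √1.04 = 1.020. The square of the factor is the matching inflation of the full trial's N.

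| Intubated (K) | P(shares differ by ≥10 points) | P(≥15 points) | SD of difference in shares | Chance error, g = 0.5 | Pooled SD factor, g = 0.5 | N factor, g = 0.5 |
|---|---|---|---|---|---|---|
| 20% (15) | 0.359 | 0.123 | 0.0986 | ±0.097 SD | 1.020 | 1.040 |
| 30% (22) | 0.425 | 0.183 | 0.1123 | ±0.110 SD | 1.026 | 1.052 |
| 50% (38) | 0.469 | 0.226 | 0.1233 | ±0.121 SD | 1.031 | 1.063 |

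Over the same shares, g = 0.25 gives a chance error of ±0.05 to 0.06 SD and SD inflation of 0.5% to 0.8%. With g = 1.0 these are ±0.19 to 0.24 SD and 8% to 12%.

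**Step 4: scale.** The standard error of the difference at 25 versus 50 is √(1/25 + 1/50) = 0.245 SD. A 15-point imbalance with a 0.5 SD gap shifts the estimate by 0.15 × 0.5 = 0.075 SD, and 0.075/0.245 = 0.31 of a standard error. For roughly normal data, the relative sampling error of an SD on 73 degrees of freedom is 1/√(2 × 73) = 8.3%, larger than the 2% to 3% inflation.

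**Step 5: what by-airway results could show.** At 20% intubated, the expected intubated counts are 5 control and 10 sufentanil. The standard error of the effect is √(1/5 + 1/10) = 0.548 SD in intubated patients and √(1/20 + 1/40) = 0.274 SD in mask patients. The difference between the two effects has standard error √(0.548² + 0.274²) = 0.612 SD. The difference detectable with 80% power is 2.80 × 0.612 = 1.7 SD. At 50% intubated it is 1.4 SD.

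**The case against.** The case against is substantial, and most of it stands as a limit on the size of the point.

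- **Unstratified randomization is valid.** It is an explicit choice in a small pilot. A reader might infer that airway confounds the comparison. It does not: each lead time applies to tablet and placebo alike, and the unadjusted confidence interval already covers chance imbalance.
- **The link to the outcomes is inference.** A reader might take the protocol to say that airway type drives postoperative opioid need. It says only that the analgesic threshold differs, as the reason for timing a tablet before induction. Nothing in it connects airway to PACU fentanyl or recovery times.
- **Two regimens blurred into one.** A reader might infer that the pooled effect is uninterpretable, or that one 25-patient control arm is stretched over two interventions. Controls follow the same timing rule, and the difference is about 15 minutes against analgesia that the protocol describes as lasting up to 3 hours. It can be read as one regimen with an airway-dependent timing rule. Something does remain here. The control tablet is inert and control fentanyl is given at induction, so lead time acts pharmacologically only in the sufentanil arm and the effect could differ by airway. Step 5 shows that this pilot could not establish such a difference.
- **The airway mix may be reported anyway.** The baseline comparison does not exclude airway; the plan is silent.
- **A Wilcoxon test takes no covariate.** This is correct, so the secondary analyses need a change of method and not just an added term.

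None of this is a reason to leave the factor unused. It is binary, known before dosing, and tied to analgesia by the protocol itself. The pilot's products are the effect and SD that adjustment would sharpen, and the plan also tests at 0.05 and 0.025.

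**Conclusion.** The point holds as a cheap improvement in precision. Randomization ignores planned airway and so do the comparisons, although the protocol gives a reason to use it. The size is modest: with 20% to 50% intubated and a 0.5 SD gap, about ±0.10 to 0.12 SD of chance error and 2% to 3% inflation of the pooled SD (4% to 6% in the full trial's N). Both inputs are assumptions. If nearly all patients have one airway, or the gap is small, the gain is close to nil; with a 1.0 SD gap the figures roughly double for chance error and about quadruple for SD and N inflation.

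The documents do not support a claim of bias, of invalid randomization, or of a pilot that fails because it pools two lead times. Nor do they make stratification necessary: adjusting for planned airway recovers most of the benefit.

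**What to change.** 1. Record planned airway (laryngeal mask or endotracheal tube) for every patient before allocation, and in any case before the tablet is dispensed. Use planned rather than actual airway in the analysis, because the actual device could change after dosing.
2. For the primary outcome, pre-specify a linear model with treatment and planned airway, on the raw or log scale as the plan already allows. Report the residual SD alongside the pooled SD, so that the full trial can be sized with or without airway adjustment.
3. For the two secondary times, use a linear model with airway or, where a rank method is needed, an airway-stratified (van Elteren) test. That test gives no estimate, so the difference and 95% interval that the plan promises need a matching airway-stratified estimator.
4. List planned airway by arm in the baseline table.
5. Label any by-airway effects or SDs as descriptive only.
6. Optionally, if the list is not yet in use, stratify it by planned airway. If it is in use, items 1 to 5 suffice.

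The cost is one degree of freedom, some analysis wording, and the need to record the airway plan before allocation. N stays at 75, and no dose or lead time is affected.

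### Time to first request for analgesia (exploratory): the event rule can miss or postdate fentanyl given at a pain score of exactly 4, and the planned median difference has no rule for patients who never have the event

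*Combined protocol and SAP*

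**What the plan says.** - **Event.** Measurements, item 9: time to first request for analgesia is "defined as the time from official case end until the first recorded Verbal Response Pain Score of greater than 4 (necessitating intervention".
- **When analgesia may be given.** Standardized Anesthetic Regimen: "For pain in the range of 4-10", a 25 µg dose of "IV fentanyl can be given at 5-minute intervals". For lower scores, "Patients will be given 500 mg acetaminophen for reported pain scores in the range of 1-3".
- **Observation.** Post-Operative Recovery Assessments: pain is scored "every 15 minutes for the first hour after PACU admission and then 30 minute intervals until PACU discharge". No later pain score is planned.
- **Analysis.** Data analysis: "the difference in time to first request for analgesia will be summarized as median difference with 95% confidence interval". The section names a t-test or Wilcoxon test for the two time-based secondary outcomes. It mentions no censoring, Kaplan-Meier estimate, assigned value or exclusion for this endpoint, and no other section supplies a rule.
- **Expected effect.** Background and Rationale describes sublingual sufentanil as "typically providing effective analgesia lasting up to 3 hours".
- **Status.** The endpoint is exploratory and carries no alpha. Randomization is 25 placebo to 50 sufentanil.

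**The concern.** There are two separate gaps.

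First, the event is a score above 4, described as the score that calls for intervention, but the regimen permits fentanyl one point lower. A patient treated at exactly 4 has received opioid analgesia without an event. That dose may itself keep later scores at 4 or below, so the event is recorded late or never.

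Second, a patient who leaves PACU without exceeding 4 has no event time, and a plain median difference needs a decision about that patient. If such patients are dropped, the comparison is between post-randomization subsets, and the patients with the best pain control are the ones removed. If they are kept, a median may not be reached. The same data can therefore give different answers depending on a choice the plan leaves open.

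The pilot is meant to supply effect estimates for planning a larger trial, so an unstable estimate would matter if this endpoint were carried forward.

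**Working it through.** The plan gives no event rate, expected median or length of stay for this endpoint, so it has no figure of its own to reproduce. From the documents I use only the arm sizes (25 and 50), the thresholds and the end of observation. All other inputs are assumptions, shown as a range.

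**1. How many patients could the threshold touch?** Assume 70% of the 75 patients reach a score of 4 or more, and 5% to 30% of first eligible scores are exactly 4. Then 75 × 0.70 × 0.05 = 2.6 and 75 × 0.70 × 0.30 = 15.8, or about 3 to 16 patients.

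**2. Effect of the threshold on the median difference.** Take exponential event times with mean *m*, and ignore discharge. If a share *f* of an arm is treated at 4 and never exceeds 4, the arm's median is −*m*·ln(1 − 0.5/(1 − *f*)). For means of 60 (control) and 120 min (sufentanil) the true difference is (120 − 60)·ln 2 = 41.6 min.

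- *f* = 0.1 in both arms: 97.3 − 48.7 = 48.7 min (from unrounded medians).
- *f* = 0.3 control, 0.1 sufentanil: 97.3 − 75.2 = 22.1 min.
- *f* = 0.1 control, 0.3 sufentanil: 150.3 − 48.7 = 101.7 min (from unrounded medians).

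If instead all of these patients exceed 4 thirty minutes later (simulated, 2 million draws per arm), the three results are 41.2, 34.4 and 47.7 min. The difference can move either way.

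**3. Effect of dropping patients without an event.** With a common stay *C*, the event share is *p* = 1 − exp(−*C*/*m*), and the median among patients with an event is −*m*·ln(1 − *p*/2). For 60 vs 120 and *C* = 90: *p* = 0.777 and 0.528, medians 29.50 and 36.75, difference 7.2 min.

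| Stay (min) | 60 vs 120 (true 41.6) | 20 vs 40 (true 13.9) |
|---|---|---|
| 60 | 3.5 | 6.8 |
| 90 | 7.2 | 10.1 |
| 120 | 11.6 | 12.0 |
| 180 | 20.3 | 13.4 |

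Rounding times up to the protocol's scoring grid gives 3.1/6.9/11.9/25.0 and 9.0/10.9/12.4/14.0. The loss is large when events are slow and stays short, and negligible when nearly all patients have early events.

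**4. Chance that a median is not reached if everyone is kept.** Count a median as reached with 13 of 25 or 25 of 50 events. The chance that at least one is unreached is 1 − (1 − P[X ≤ 12 of 25])(1 − P[Y ≤ 24 of 50]).

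- 60 vs 120, stays of 60/90/120/180 min: 92%/30%/2%/0%.
- 20 vs 40: 0% throughout.
- Equal event shares of 40/50/60/70/80%: 98%/72%/20%/2%/0%.

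**5. What censoring at discharge recovers.** Means 60 vs 120, stays uniform on 60–180 min, 4,000 simulated trials. If stay is independent of pain, the Kaplan-Meier difference averages about 41 min, with both medians reached in 99.6% of trials; dropping non-events gives about 11 min. If patients with no event by 60 min leave at 60–90 min, both medians are reached in only about 56% of trials, and the difference in those trials averages about 30 min. Censoring is better than dropping, but the 41-minute figure belongs to a favourable case and is not a validation.

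**The case against.** Item 9 is a complete, measurable rule, and an investigator may set an event threshold above the score at which as-needed treatment becomes permissible. A reader might infer that the two sections contradict each other on care. They need not, because the regimen's wording on fentanyl is permissive. What stands is a measurement mismatch: the endpoint's name and its remark about intervention do not fit a rule that passes over fentanyl given at 4.

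A reader might also infer from the Background that many sufentanil patients will leave without an event. The documents do not show this. The stated duration runs from a tablet given about 15 or 30 minutes before induction, whereas the endpoint's clock starts at case end, so the pre-induction wait and surgery use up part of it. It also concerns one arm only. Events may be missing in either arm, but how often is unknown.

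Nor does the plan say that non-events will be dropped; that is one way of filling a silence. If nearly every patient exceeds 4 early in PACU, the second gap has almost no effect.

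Finally, the first fentanyl dose is a different construct and not a clear correction. It measures as-needed dosing, overlaps the primary outcome and leaves out acetaminophen.

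These arguments limit the weight of the point. They do not supply the missing rule for patients without an event, or make the score-above-4 event record fentanyl given at 4.

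**Conclusion.** The concern holds as a minor point about one exploratory endpoint. Both parts rest on the text alone: the event can miss or postdate fentanyl given at exactly 4, and no rule says how patients without an event by PACU discharge enter the median difference.

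The size is not determined by the documents. Every figure above depends on assumed exponential times, stays and shares treated at 4, and the range runs from negligible to most of a real delay. Dropping non-events can shrink a delay. The threshold effect has no fixed direction. The documents do not support a claim of a known bias, a known frequency of non-events or an error in care. The primary outcome, cumulative fentanyl from the Medication Administration Report, and both secondary outcomes are unaffected.

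**What to change.** 1. Reconcile Measurements item 9 with the Standardized Anesthetic Regimen so that the endpoint's event matches the point at which analgesia is given, without changing care. One option is the time of the first PACU fentanyl dose in the Medication Administration Report, already the source for the primary outcome's "dose of fentanyl received between arrival to and discharge from PACU per patient". If it is chosen, state its limits as given above.
2. Keep all randomized patients and treat those without an event as censored at PACU discharge.
3. Make Kaplan-Meier curves by arm and the event-free proportion at discharge the main summary. Give the median difference with its confidence interval only where both medians are reached.
4. Add one sensitivity analysis with never-events ranked last, because discharge time may depend on pain as well as on treatment.

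The cost is two or three sentences of wording and slightly more analysis. The first-dose option also requires extracting dose times, since the plan specifies only the cumulative dose. With short stays the median difference may go unreported, leaving the curves and event-free proportions.
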